addressing the transfer of acquired skills (e.g. UE motor capacity) to the performance of UE tasks during activities of daily living (ADL). The ALPS protocol will be relevant to clinical practice because it will provide clinicians with a structured, patient-centered motor learning approach to facilitate use of the paretic arm and hand. In addition, comparisons between our two intervention groups (robot-assisted therapy vs. robot-assisted therapy [RT] and task-oriented training [RT-TOT]) will add to our scientific knowledge of whether the combination of robot therapy and therapist-directed task-oriented training provides added benefit to RT alone. We will examine participant outcome measures across domains of the International Classification of Functioning (ICF)¹¹ to provide insights regarding mechanisms that underlie the recovery of motor function after stroke.

II. Specific Aims

The specific aims of this pilot study are:

Aim 1: To develop and refine a structured Active Learning Program for Stroke (ALPS) that integrates motor learning strategies with a patient-targeted home action plan to be used with either 1) robot-assisted therapy (RT) or 2) combined robot-assisted therapy and task-oriented training (RT-TOT) for the paretic arm and hand after stroke, in preparation for a larger clinical trial.

Hypothesis 1.1: RT and combined RT-TOT protocols that incorporate ALPS training will be feasible and well-tolerated by participants.

Hypothesis 1.2: After intervention, participants in both treatment groups will identify and implement a greater number of motor learning strategies during UE tasks in clinic and home settings and will report increased self-efficacy as measured by the Confidence in Arm and Hand Movement (CAHM) scale.

Aim 2: To examine effects of ALPS training and a patient-targeted home action plan combined with either 1) RT or 2) RT-TOT on paretic UE motor capacity and performance during daily activities, using *outcome measures across ICF domains*.

Hypothesis 2.1: Compared to RT alone, RT-TOT will yield similar outcomes on clinical measures of UE motor capacity (e.g. Fugl-Meyer Assessment, Wolf Motor Function Test), but greater gains on measures of UE function in the home and community (e.g. Motor Activity Log, UE accelerometry data via wearable sensors).

III. Subject Selection

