Specifically, the informed consent will be obtained by the principal investigator ([name]) or [name], Research Coordinator/Manager in the Motion Analysis Lab at SRH. The testing and intervention protocol will be described and the research space and equipment will be shown to the subject. Study staff will clearly explain all procedures and risks of the protocol outlined in the informed consent form (ICF). The subject will be given adequate time to consider his/her decision and encouraged to ask questions, both during the initial interview and throughout the study. A member of the study staff will answer any questions regarding the study at the time consent is given. Enrollment will begin when the subject thoroughly understands and signs the informed consent form. Participants will be provided with a signed copy of the completed consent form. Once enrolled, the subject may pause or terminate his/her participation at any time during the study. Participants will be randomized to one of two treatment groups (robot-assisted therapy [RT] or robot-assisted therapy plus task-oriented training [RT-TOT]) according to a randomization sequence prepared by [name].

V. Study Procedures

Study procedures will occur in the Motion Analysis Lab (MAL). The study involves up to 24 visits in total to be completed within a 16 week period. The total duration may vary within this 16 week period to accommodate missed study visits.

1. MAL Visit Day 1: Screening and enrollment
2. MAL Visit Days 2-3: Baseline outcomes assessment battery. We will equip participants with Actical wearable sensors for home-based accelerometry data collection.
3. MAL Visit Days 4-21: Intervention. We will retrieve Actical wearable sensors at after baseline data collection at the onset of intervention visits.
4. MAL Visit Days 22-23: End-of-intervention outcomes assessment battery. We will equip participants with Actical wearable sensors for home-based accelerometry data collection.
5. MAL Visit Day 24: Follow-up outcomes assessment battery. We will equip participants with Actical wearable sensors for home-based accelerometry data collection.

Schema 1: study procedures flow

- 1) MAL Visit Day 1: Screening and enrollment** (procedures described in section IV)
- 2) MAL Visit Days 2-3: Baseline outcomes assessment battery** (administered within a 2-3 week period before intervention). **Equip with Actical wearable sensors.**

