Surface electromyographic (SEMG) data may be gathered during the kinematic testing protocol above to study the characteristics of muscle activation patterns in stroke survivors during the performance of arm reaching movements. Data will be collected using Cometa WavePlus wireless surface electrodes with 16 channels (www.cometasystems.com) for the detection of EMG activity from muscles that are involved in the performance of upper extremity movements. We will follow the SENIAM (Surface Electromyography for the Non-Invasive Assessment of Muscles) guidelines to place electrodes on several muscles involved in the performance of the arm reaching movements. Muscles may include the following: rhomboid major, latissimus dorsi, infraspinatus, superior trapezius, deltoid - anterior part, deltoid - medial part, deltoid - posterior part, pectoralis major, clavicular head, triceps brachii, lateral/medial heads, biceps brachii (short heads), biceps brachii (long heads), brachialis, brachioradialis, pronator teres, extensor carpi radialis and extensor carpi ulnaris. The EMG on the back, shoulder, upper arm and forearm will be attached using bio-adhesive double sided tape and secured with Coban.

We may ask permission from study participants to video record them during the performance of the above-described clinical tests and the lab-based assessments.

Home Based Accelerometry – Wearable Sensors: The Actical physical activity monitoring system (<http://www.philips.com>) is a multi-directional, waterproof sensor used to quantitatively measure UE activity during everyday living situations. Sensors will be worn on both wrists during 72-hour periods at each assessment point to allow comparisons between paretic and intact UE activity in the home/community.¹⁹ A single page user guide for the wrist sensors will be provided to participants, and sensors may be removed at any time due to discomfort. There will be no penalty for loss or damage to a wrist sensor, subjects will be given a pre-stamped envelope to return the Actical at the end of the 72-hour period. Staff in [name] Analysis Laboratory (MAL) at SRH have used this device and will analyze de-identified raw data in order to examine changes in arm movement pre- to post-intervention (e.g. the amount and laterality of use).

The proposed assessment timeline is below (Table 1).

ICF Domain/Assessments	Baseline	Discharge	1-month Follow-up
UE Function:			

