Fugl-Meyer Assessment – UE, pain, sensation subtests ^{20,21}	X	X	X
Modified Ashworth Scale ²²	X	X	X
MAL: 3-D motion capture/SEMG analysis UE reach/grasp	X	X	
Activities & Participation:			
Wolf Motor Function Test ²³	X	X	X
Motor Activity Log ²⁴	X	X	X
Stroke Impact Scale ²⁵	X	X	X
Confidence in Arm & Hand Movement (CAHM) ²⁶	X	X	X
Home-Based Accelerometry/Wearable Sensors	X	X	X

Table 1. Assessment Timeline.

3) MAL Visit Days 4-21: Intervention. Retrieve Actical wearable sensors.

Participants will be randomly assigned to one of two treatment groups:

- A. Robot-Assisted Therapy (RT) + ALPS protocol to enhance active problem solving, confidence in UE use, and transfer of training to functional UE tasks, and all will be provided a home action plan.
- B. Robot-Assisted Therapy (RT) + Task-Oriented Training (TOT) + ALPS protocol to enhance active problem solving, confidence in UE use, and transfer of training to functional UE tasks, and all will be provided a home action plan.

Robot-Assisted Therapy (RT): Participants will receive robot-assisted UE therapy using two commercially-available rehabilitation devices available for use at SRH: the Armeo@Spring (Hocoma AG, Switzerland) and Amadeo (Tyromotion, Graz, AU)(Figure 1). The Armeo@Spring is a passive exoskeletal spring suspension system that provides repetitive practice of virtual goal-directed reaching tasks for the paretic UE. A distal sensor that detects grasp pressure allows the grasp/release of virtual objects during games. The amount of gravity assist and virtual task demands are adjusted by the clinician to provide challenging yet achievable movement therapy. During the first treatment session, the Armeo@Spring will be adjusted for the participant’s arm size and required angle of suspension (approximately 45° shoulder flexion, 25° elbow flexion) and the workspace will be measured via standard procedures.

The Amadeo robotic system provides position-controlled exercises during computerized games that emphasize grasp and release of the paretic hand. Participants will be seated comfortably with the forearm/wrist strapped to an adjustable splint attached to the robot device with the wrist

in approximately neutral position. A small magnetic disc is secured to the distal phalanx of each

Figure 1. Armeo and Amadeo.

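### The 72-hour accelerometry windows are not matched on day of the week within participant, which adds avoidable (probably modest) noise to change in amount of arm use

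*Combined protocol and SAP*

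**What the plan says.** Hypothesis 2.1 (Section II) expects the combined robot and task-oriented arm to show "greater gains on measures of UE function in the home and community (e.g. Motor Activity Log, UE accelerometry data via wearable sensors". Table 1 lists "Home-Based Accelerometry/Wearable Sensors" at baseline, discharge and 1-month follow-up.

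The accelerometry paragraph of Section V states: "Sensors will be worn on both wrists during 72-hour periods at each assessment point", with the purpose "to allow comparisons between paretic and intact UE activity in the home/community". It adds that "sensors may be removed at any time due to discomfort", and that laboratory staff will work from raw data to "examine changes in arm movement pre- to post-intervention (e.g. the amount and laterality of use".

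On timing, Section V says the baseline battery is "administered within a 2-3 week period before intervention". It also says: "The total duration may vary within this 16 week period to accommodate missed study visits". Missed sessions may move to the next day or week. Sensors are fitted at the assessment visits.

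No section fixes the weekday on which wear starts, asks for an on/off record, or defines valid wear. Section VI plans a 2 group x 3 time-point repeated measures ANOVA for each outcome, with no term for calendar or wear time.

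**The concern.** The quantity of interest is each participant's change between windows. If daily routine differs between weekdays and weekends, part of that change reflects which days were sampled and not what the therapy did. Three days is short enough for the weekend share to vary widely from one window to the next.

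Accelerometry is the only sensor-based home measure in Table 1, and the other named home measure, the Motor Activity Log, is a different kind of instrument. The pilot is also meant to prepare a larger trial, and its data may feed that trial's power analysis. Avoidable variance would carry into that calculation.

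A second, smaller matter is that sensors may come off for discomfort and the plan does not say how unworn time is handled. For a comparison of two arms, one-sided removal matters most.

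**Working it through.** The plan gives no accelerometry variance, effect size, alpha or power figure, so there is nothing of its own to reproduce. What follows is illustration.

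**Inputs from the documents:** 72-hour windows, both wrists, three assessments; up to 20 participants.

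**Assumptions:** fitting at noon, Monday to Friday, each day equally likely and independent between assessments; 1:1 allocation (10 per arm); two-sided 5% test; 48 waking hours in 72. None of these is in the documents.

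**Step 1. Weekend hours by start day**

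| Start (noon) | Weekend hours of 72 | Share |
|---|---|---|
| Monday | 0 | 0 |
| Tuesday | 0 | 0 |
| Wednesday | 12 | 0.167 |
| Thursday | 36 | 0.500 |
| Friday | 48 | 0.667 |

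Mean share = (0 + 0 + 0.167 + 0.500 + 0.667)/5 = 0.267. Variance = (0 + 0 + 0.0278 + 0.2500 + 0.4444)/5 − 0.267² = 0.0733. Monday and Tuesday share a value, so two windows differ in weekend share with probability 1 − (0.4² + 3 × 0.2²) = 0.72.

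**Step 2. Extreme shift in amount of use.** If weekend use differs from weekday use by 10% to 20% (assumed), moving from a Monday to a Friday start shifts the 72-hour mean by 48/72 × 10% to 20% = 6.7% to 13.3%. This is the worst pair of days, not a typical one.

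**Step 3. Noise in the change score.** Let w be the weekend-weekday difference in units of the SD of change with matched windows. Two independent windows inflate the variance of change by 1 + 2 × w² × 0.0733. Power is for a two-sample t test on change at a standardised effect of 1.0, a simplification of the planned ANOVA.

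| w (assumed) | Variance inflation | Power |
|---|---|---|
| 0 (matched) | 1 | 56.2% |
| 0.25 | 1.009 | 55.8% |
| 0.5 | 1.037 | 54.7% |
| 1.0 | 1.147 | 50.7% |

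The loss is 0.4 to 5.5 points. For scale, 10 per arm needs an effect of about 1.32 for 80% power, so sample size limits power far more than the calendar does.

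**Step 4. The ratio.** If weekends multiply use of both arms by the same factor, that factor appears in numerator and denominator and cancels. Only a weekend change in laterality itself would remain.

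**Step 5. Unworn time, if it were scored as zero movement.** With a true paretic-to-intact ratio of 0.60 and 2 to 12 of 48 waking hours unworn:
- paretic sensor off: 0.60 × 46/48 = 0.575, down to 0.60 × 36/48 = 0.45;
- intact sensor off: 0.60 ÷ (46/48) = 0.626, up to 0.60 ÷ (36/48) = 0.80;
- both off together: the ratio stays at 0.60;
- amount recorded by an unworn sensor: down 2/48 = 4.2% to 12/48 = 25.0%.

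**The case against.** The strongest reply is that this is a pilot of at most 20 people with no designated primary outcome or power target, and that weekday matching is an operational preference whose benefit cannot be derived from the documents. The second half of that stands: every magnitude above is assumed, and the gain is modest.

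Three stronger readings are tempting, and the documents do not support them.

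- A reader might infer that the mismatch biases the comparison. Participants are randomised, and nothing suggests that fitting days differ by arm. Without that, the mismatch is noise.
- A reader might infer that a removed sensor is counted as no arm use. The plan does not say so. Staff hold the raw data and have used the device, so they could screen out unworn time. Removal is allowed only for discomfort, the device is waterproof, a user guide is supplied, and Section VII provides softer strapping for sensitive skin. Even if unworn time were scored as zero, the group contrast would be biased only if removal, or its change over time, differed by arm.
- A reader might infer that the mismatch is beyond repair once data are collected. Recorded dates would allow the weekend share to be calculated. However, that share varies within person over time and does not fit simply into the planned 2 x 3 ANOVA. Adjustment would need a different model in at most 20 people, so matching by design is the better route.

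**Conclusion.** The point holds as a minor design improvement. The plan leaves the weekend content of a participant's three windows to chance. On assumed noon weekday starts, that content ranges from 0 to 48 of 72 hours. This adds noise, not bias, to within-person change in amount of use. The power cost is 0.4 to 5.5 points at a standardised effect of 1.0, for assumed weekend differences of 0.25 to 1.0 SD of change and 10 per arm. It is probably smaller for a paretic-to-intact ratio.

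The non-wear point is secondary and mostly one of missing detail: the plan is silent, so nothing rules out one-sided removal being read as no use. The figures in Step 5 show what would follow if that happened. They do not show that it will.

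**What to change.** Start each participant's 72-hour wear on the same weekday, at about the same clock time, at baseline, discharge and follow-up. Baseline and discharge each have two visit days, which gives some choice. Follow-up has one, so either book it on the matching weekday or issue the sensors with an agreed start day. Any delayed baseline start must leave the full 72 hours before the first intervention session. Do not add a weekend-share covariate.

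For non-wear, give participants a brief on/off log for each wrist. Compute the laterality ratio over time when both sensors are worn, and report it alongside amount of use, which the plan also names, and not in its place. The log is preferable to a rule based on movement alone, which could mistake true stillness of the paretic arm for non-wear and inflate the ratio.

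The cost is a small scheduling constraint, a one-page log and one processing rule. No visits are added and the planned ANOVA is unchanged.

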digit for connection to the robotically controlled slide that guides movement. Each one hour session will include visually evoked games that provide active-assistive training of collective, sequential and individual flexion and extension of the digits as well as isometric flexion/extension contractions. Rest periods will be offered between games, as needed. Task challenge for each training device will be incrementally increased or decreased based on participant performance.

All participants will receive 1 hour sessions, 2-3x/week for 6-9 weeks (total 18 sessions), divided into two 9 session treatment blocks. The two treatment blocks will be given in order, with all participants receiving proximal training via Armeo@Spring during the first block followed by Amadeo distal training during block 2. All training sessions for one treatment block will be completed before proceeding to the next. The robot training sessions will follow standard protocols that provide highly repetitive movement training, and the number of games/repetitions completed in each session will be recorded. Participants may miss up to 3 appointments, and we will reschedule the following day or week at a time that is mutually convenient. Participants who miss 4 consecutive appointments may be removed from the study.

Active Learning Program for Stroke (ALPS): ALPS development and implementation will be based upon principles of experience dependent neuroplasticity as described by Kleim & Jones,⁹ empirical evidence from UE motor learning and task-oriented training programs for individuals with stroke,^{10,27,28} and a conceptual framework for integrating skill, capacity and motivation as described in multiple publications by Winstein et al.^{10,29,30} While principles of repetition, intensity, and specificity of training are active ingredients of the RT and RT-TOT protocols to improve motor capacity, other motor learning constructs have not been well-infused into prior robot training programs. These constructs will be implemented during RT and RT-TOT sessions and will be an integral component of the home action plan. Preliminary examples of protocol components are highlighted in Table 3 below.

Motor Learning Principles	Example
Use it or lose it ^{9,10,27}	Identify interfering and changeable impairments Provide targeted UE training based on individual's motor capacity
Saliency of training tasks ^{9,10}	Establish clear patient-centered goals

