The tasks selected for the home action plan (HAP) will be based on the participant's identified upper extremity (UE) goals and/or therapist input based on a) the current focus of robot therapy (i.e. shoulder/elbow, hand) and b) scores on the FMA key form. Because of this participant-centered approach there will be no core tasks included in every HAP, however, similarities may be observed across individuals. Participants will identify an UE task to be completed at home and the ALPS strategy or strategies they will use to facilitate performance weekly. A brief self-report questionnaire to collect ordinal data on ALPS strategy use, HAP performance, frequency, & perceived difficulty will be administered by research staff after every 3rd therapy session. Participant's engagement in the home action plan will be rated using a 3 point Likert type scale²⁹ and patient-targeted UE tasks will be updated as needed. A similar questionnaire will be administered during the follow-up assessment to gain information regarding the participant's engagement in home practice after formal therapy has ended. Participants will be instructed that completion of the HAP is voluntary and will not affect their therapy in any way. The intent of the HAP is to provide documentation of home carry-over. It is not designed to be a comprehensive home exercise program.

4) MAL Visit Days 22-23: End-of intervention outcomes assessment battery
(administered at discharge assessment after 18 treatment sessions) **Equip with Actical wearable sensors.**

The same assessment battery as the one performed at baseline will be re-administered.

5) MAL Visit Day 24 (Final Visit): Follow-up outcomes assessment battery
(administered at 1 month post-therapy) **Equip with Actical wearable sensors.**

The same assessment battery as the one performed at baseline will be re-administered, **except for** the Motion Capture and EMG analysis.

VI. Biostatistical Analysis

Separate repeated measures analyses of variance (2 group x 3 time points) will examine changes in scores for each outcome measure across a) baseline, b) discharge and c) follow-up assessments. Descriptive statistics will be used to compare key group characteristics, including age, hand dominance, side of lesion, and years of education. Group comparisons will be assessed by chi-square analyses for categorical data and t-tests for continuous data. The data collected from this pilot study may be used for a power analysis of a larger clinical trial.

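### The attendance rule can take randomised participants out of the study, and the plan does not provide for assessing anyone who stops short of 18 sessions, so their post-baseline outcomes may be lost

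*Combined protocol and SAP*

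**What the plan says.** The intervention part of V. Study Procedures plans the course of therapy as follows: "All participants will receive 1 hour sessions, 2-3x/week for 6-9 weeks (total 18 sessions), divided into two 9 session treatment blocks". Two sentences on attendance follow. The first is tolerant: "Participants may miss up to 3 appointments, and we will reschedule the following day or week at a time that is mutually convenient". The second sets the removal rule: "Participants who miss 4 consecutive appointments may be removed from the study". No criterion is given for using that discretion, and nobody is named to exercise it.

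The later assessments are placed relative to therapy. The end-of-intervention battery is "administered at discharge assessment after 18 treatment sessions", and the follow-up battery is "administered at 1 month post-therapy". Neither has a calendar alternative for a participant whose therapy ends early. The opening of the same section gives the outer limit: "The study involves up to 24 visits in total to be completed within a 16 week period". It allows the duration to vary inside that window so that missed visits can be made up.

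VI. Biostatistical Analysis plans one model per outcome: "Separate repeated measures analyses of variance (2 group x 3 time points) will examine changes in scores for each outcome measure". It names no analysis set and no method for missing data.

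**The concern.** Attendance is observed after randomisation and may be affected by the assigned treatment. A rule that acts on it and ends participation in the study, rather than therapy alone, can make outcome data missing selectively. The decision is discretionary. The documents describe only the clinical evaluator as blinded, so whoever decides on removal may know the arm.

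Two things are at stake:

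- **The arm comparison (Hypothesis 2.1).** If removed participants have no discharge or follow-up scores, a standard repeated measures ANOVA drops them and compares those who completed. If better attenders improve more, gains within an arm are overstated. If removal differs between arms, the RT-TOT versus RT contrast shifts as well.
- **Use of the pilot data.** The analysis section says the data may feed a power analysis for a larger trial. Gains measured in completers only could be carried into that calculation.

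The point is separate from the choice of model. A different model cannot supply scores that were not collected, whereas a change to conduct can secure them.

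**Working it through.** The plan gives no power, SD, dropout rate or allocation ratio, so it has no figure to reproduce. The check has two parts: a reading of the rules together, and an illustration on stated assumptions.

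**Reading the rules together**

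| Situation | What the plan provides |
|---|---|
| Up to 3 misses | Rescheduled, so 18 sessions and a discharge battery can still be reached |
| 4 or more misses, not consecutive | Not addressed |
| 4 consecutive misses | May be removed from the study; later assessment not addressed |
| Voluntary early stop (IV. Subject enrollment) | Allowed at any time; later assessment not addressed |

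At 2 to 3 sessions a week, four consecutive misses amount to 4/3 = 1.3 to 4/2 = 2 weeks of absence. A removed participant would have baseline scores and any home-plan questionnaires already given (one after every third session), but those questionnaires are not the outcome battery.

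**Calendar**

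Baseline of 2 to 3 weeks, therapy of 6 to 9 weeks and about 4 weeks to follow-up give 2 + 6 + 4 = 12 to 3 + 9 + 4 = 16 weeks. Three make-up sessions add 3/3 = 1 to 3/2 = 1.5 weeks. The slowest schedule therefore fills the 16-week window before any session is made up. A fallback assessment date has to be chosen with this in mind.

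**Illustration of bias**

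Assumptions, none of them from the documents:

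- 10 per arm (up to 20 participants, 1:1)
- attendance propensity and outcome change jointly normal, with correlation ρ = 0.3 to 0.5
- the worst-attending 20% of one arm lost, and none of the other

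The upward shift in the retained mean is ρ × φ(c)/(1 − r). With r = 0.20, c is the 20th percentile of the standard normal, φ(c) = 0.280, and 0.280/0.80 = 0.350.

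- ρ = 0.3: 0.3 × 0.350 = 0.105 SD
- ρ = 0.5: 0.5 × 0.350 = 0.175 SD

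Cross-check: bias also equals the share removed times the gap between retained and removed means. That gap is ρ × (0.280/0.80 + 0.280/0.20) = ρ × 1.75, or 0.525 to 0.875 SD. Multiplying by 0.20 returns 0.105 to 0.175 SD.

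If both arms lose the same share with the same correlation, each gain is inflated by 0.105 to 0.175 SD, and the difference between arms has an expected bias of zero.

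**Illustration of precision**

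The 95% half-width for the arm difference, in SD units, is t(0.975, n₁ + n₂ − 2) × √(1/n₁ + 1/n₂).

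| Arms | Half-width |
|---|---|
| 10 v 10 | 2.101 × 0.447 = 0.94 |
| 8 v 10 | 2.120 × 0.474 = 1.01 |
| 8 v 8 | 2.145 × 0.500 = 1.07 |

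The 8 v 10 row goes with the one-arm loss used for the bias. The 8 v 8 row is a different scenario, in which both arms lose two participants.

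**The case against.** The strongest reply is that the documents are silent rather than prohibitive. Removal is permitted, not required, and only after four consecutive misses. Up to three misses are rescheduled, and the duration may vary within the 16 weeks, so the plan tries to bring irregular attenders to 18 sessions and a discharge visit. The timing of the batteries describes the standard course and does not forbid assessing others. All of this stands. A reader might infer that poor attenders in general are removed, or that their outcomes will never be collected. The text does not say either.

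A reader might also infer that no analysis could keep these participants. That is too absolute. A likelihood-based mixed model or multiple imputation could retain them through their baseline scores under missing at random. However, no such method is planned, the assumption is doubtful if attendance is related to outcome, and a participant with baseline data only adds almost nothing about later differences between arms.

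The bias is conditional. Loss from one arm only is the most adverse split, and the documents give no reason to expect it: session length and frequency are the same in both arms, which differ in 20 to 30 minutes of content per session. Even then, the bias is small beside the uncertainty of the comparison: 0.105/0.94 = 11% to 0.175/0.94 = 19% of the half-width with full data.

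Finally, a removal is itself a feasibility result under Hypothesis 1.1, and nothing says that removals go uncounted. What remains is that the plan does not secure outcomes for anyone who is removed or stops early.

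**Conclusion.** The point holds as a risk created by a stated conduct rule. A participant may be taken out of the study after randomisation on the basis of attendance. The later batteries are tied to completing or ending therapy, and no text provides for assessing people who are removed or stop early. If their scores are missing, the planned ANOVA becomes a comparison of completers.

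The actual size cannot be known from the documents. Under the assumed one-arm loss, the contrast is biased by about 0.10 to 0.18 SD and the half-width grows from 0.94 to 1.01 SD, or to 1.07 SD if both arms fall to 8. The direction depends on the assumed positive correlation between attendance and improvement. It would be wrong to conclude that the contrast will be biased, since similar loss in both arms would largely cancel there while still overstating both gains.

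A reader might also take the two attendance sentences to contradict each other. They do not; they leave four or more non-consecutive misses uncovered. The correction is inexpensive and worth making.

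**What to change.** - State that any attendance rule applies to therapy only and does not end outcome collection.
- Invite every randomised participant who has not withdrawn consent to the discharge and one-month batteries and to the sensor wear.
- Hold discharge after session 18. For those who stop early, hold it at a prespecified time by which therapy would have ended within the study window, allowing for rescheduled sessions, with follow-up one month later. The date must be defined so that it does not cut off a participant who is still making up sessions. The calendar above shows no slack on the slowest schedule.
- Analyse all participants in the arm to which they were assigned.
- Clarify what happens after four or more non-consecutive misses. No position is taken here on the therapy rule itself.

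The cost is a few sentences of protocol text and visits the schedule already contains: visit days 22 to 24, three per participant, so six if two participants stopped early. The downside is a few assessments of people who did not receive the full course of therapy.
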